9.2.3 Serious Adverse Event Definition

A Serious Adverse Event (SAE) is any untoward medical occurrence (whether considered to be related to investigational product or not) that at any dose:

- Results in death
- Is life-threatening

NOTE: The term ‘life-threatening’ in the definition of ‘serious’ refers to an event in which the subject was at risk of death at the time of the event; it does not refer to an event which hypothetically might have caused death if it was more severe.
- Requires hospitalization or prolongation of existing hospitalization
- Results in persistent or significant disability/incapacity
- Is a congenital abnormality/birth defect
- Is an important medical event; Note: Important medical events that may not result in death, be life-threatening, or require hospitalization may be considered an SAE when, based upon appropriate medical judgment, they may jeopardize the subject and may require medical or surgical intervention to prevent 1 of the outcomes listed in this definition. Examples of such medical events include allergic bronchospasm requiring intensive treatment in an emergency room or at home; blood dyscrasias or convulsions that do not result in subject hospitalization; or the development of drug dependency or drug abuse.

Hospitalizations, which are the result of elective or previously scheduled surgery for pre-existing conditions, which have not worsened after initiation of treatment, should not be classified as SAEs. For example, an admission for a previously scheduled ventral hernia repair would not be classified as an SAE.

However, complication(s) resulting from a hospitalization for an elective or previously scheduled surgery that meets serious criteria must be reported as SAE(s).

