10.8 Safety Analyses

Adverse events will be coded using MedDRA. The number of events, incidence, and percentage of treatment-emergent adverse events (TEAE) will be calculated overall, by system organ class (SOC), and by preferred term. Treatment-emergent adverse events will be further summarized by severity and relationship to the investigational product. Adverse events related to the investigational product, AEs leading to withdrawal, SAEs, and deaths will be summarized/listed.

Clinical laboratory tests, vital signs, and ECG findings will be summarized by treatment group and visit. Potentially clinically important findings will also be summarized or listed.

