3.4.2 Secondary Endpoints

The secondary endpoints (Efficacy measures) of the study are:

- 6-minute walk test score (6MWT),
- Patient global assessment score (based on the KCCQ instrument),
- Physician's Assessment of Functional Class (measured by NYHA Functional Class assessment), and
- Incidence of clinical events (death and hospitalizations).

All Secondary Endpoint measurements will be presented in patient-level listings.

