3.5.1 Adverse Events (AEs)

Adverse events will be coded according to the MedDRA guidance version 21.0. An adverse event is considered treatment-emergent if the start date/time of the event is:

- On or after the date/time of first IV dose for IV dosing only patients and patients who transitioned to oral dosing and were in IV period,
- On or after the date/time of first oral dose for patients who transitioned to oral dosing and were in oral period.

An overview of AEs will be provided including counts and percentages of patients with the following:

- Any TEAEs (overall and by maximum severity)
- Any study drug-related TEAEs
- Any serious TEAEs (TESAEs)
- Any TEAEs leading to discontinuation of study drug
- Any TEAEs leading to discontinuation of study.

Counts and percentages of patients will also be presented by system organ class and preferred term for each of the categories in the overview. TEAEs and TESAEs will be also provided in patient-level listings.

If an adverse event has incomplete start or stop dates, dates will be imputed to determine whether the adverse event was treatment-emergent. Details on the imputation for incomplete dates will be provided in the final SAP to correspond to CRF design and instructions. Summaries will be performed by treatment/dose group.

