4 CHANGES FROM PROTOCOL-SPECIFIED STATISTICAL ANALYSES

This SAP does not deviate from the statistical analysis described in v5.0 of the protocol. Any deviations from the protocol or SAP will be described in the CSR.

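### The protocol promises the number of TEAEs, but the SAP's tables count only patients, so repeated events in the same patient show up only in the listings

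*SAP*

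**What the plan says.** Protocol v4.1, section 10.8: "The number of events, incidence, and percentage of treatment-emergent adverse events (TEAE) will be calculated overall", and the sentence goes on to the same quantities by system organ class and by preferred term.

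SAP 3.5.1 uses the patient as the unit throughout. For the overview: "An overview of AEs will be provided including counts and percentages of patients with the following". For the detailed tables: "Counts and percentages of patients will also be presented by system organ class and preferred term for each of the categories in the overview". Individual events survive in one place: "TEAEs and TESAEs will be also provided in patient-level listings" (Listings 16.2.7.1 and 16.2.7.2).

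SAP 3.2.1 splits the summaries into IV period, oral period and total. The titles of Tables 14.3.1 to 14.3.2.6 mention neither event counts nor rates per unit of exposure.

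Hospitalizations have no table of their own. SAP 3.4.2 makes death and hospitalization a secondary endpoint expressed as an incidence, and adds: "All Secondary Endpoint measurements will be presented in patient-level listings". The SAP's list of outputs, however, has no table or listing for them. They reach the tables through the seriousness criterion in protocol 9.2.3, "Requires hospitalization or prolongation of existing hospitalization", as serious TEAEs under their coded terms.

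SAP section 4: "This SAP does not deviate from the statistical analysis described in v5.0 of the protocol".

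**The concern.** Incidence and severity of adverse events is the primary endpoint, and the primary objective is safety and tolerability in extended use. Protocol 1.3.6 names hypotension and tachycardia as the main safety events of interest, and protocol 1.2 describes a population with frequent hospitalizations. Events of this kind can recur in one patient.

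A count of patients with at least one event gives a patient admitted once and a patient admitted five times under the same term the same weight within a column. Over long follow-up the broad summary rows become less sensitive to how often events happen. The protocol's event count would have shown this. The SAP drops it and states that nothing has changed, so a reader of the SAP would not know that a promised measure of the primary endpoint is missing.

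**Working it through.** **Text comparison.** The study is descriptive (SAP 3.1.5: no hypothesis testing) and the documents give no expected event rate, so there is no planned figure to reproduce.

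| Item | Protocol v4.1, 10.8 | SAP 3.5.1 and table list |
|---|---|---|
| Number of TEAEs | yes: overall, by class, by term | not specified |
| Patients with a TEAE, n (%) | yes | yes |
| Rate per patient-year | not specified | not specified |
| Individual events | – | Listings 16.2.7.1 and 16.2.7.2 |

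Counting once means once per row and per column. The same patient can be counted again under another term, or in the other dosing period.

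**Follow-up.** Patients who stay on IV are treated for up to 2 years from entry (protocol 1.1). Those who move to oral drug are planned for 3 years after the transition (protocol 4.3), in addition to their earlier IV time. Realized oral time may be shorter. SAP 3.3.5 sets the last oral dose to Feb 1, 2023 for patients not covered by its other rules, and v4.1, which introduced the transition, carries dates from January to June 2021. That allows those patients about 2 years at most. Both 2 and 3 years are therefore shown.

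**Illustration.** Assume a constant rate r per patient-year, equal follow-up T and a Poisson process. Then:

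- mean events per patient = rT
- proportion with at least one event = 1 − exp(−rT)
- share of events not reflected in a patient count = 1 − [1 − exp(−rT)]/(rT)

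| r (assumed) | At least one, T = 2 | At least one, T = 3 | Mean events, T = 2 / T = 3 |
|---|---|---|---|
| 0.1 | 18.1% | 25.9% | 0.2 / 0.3 |
| 0.2 | 33.0% | 45.1% | 0.4 / 0.6 |
| 0.5 | 63.2% | 77.7% | 1.0 / 1.5 |
| 1 | 86.5% | 95.0% | 2 / 3 |
| 2 | 98.2% | 99.8% | 4 / 6 |

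A doubling from 1 to 2 per year moves the percentage by 11.7 points over 2 years and by under 5 points over 3. A doubling from 0.1 to 0.2, which is closer to what a single preferred term might show, moves it from 25.9% to 45.1% over 3 years and is plainly visible.

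For r between 0.2 and 1.0, the share of events that a patient count does not reflect is 18% to 57% over 2 years and 25% to 68% over 3. If events cluster within patients (negative binomial, dispersion 1, proportion with at least one = 1 − 1/(1 + rT)), the shares are 29% to 67% and 38% to 75%. In absolute terms, take N = 37, the number randomized in the parent study and so an upper bound. At r = 1 and T = 2, 37 × 1 × 2 = 74 events would appear as 37 × 0.865 = 32 patients.

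**Record structure.** Protocol 9.1.1 has a change in severity entered as a new event. A raw count of records would therefore exceed the number of clinical episodes.

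**The case against.** Several objections have force.

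- **The version gap.** SAP section 4 refers to protocol v5.0, and only v4.1 was supplied. Section 10.8 may read differently in v5.0, and the separate programming specifications might add an event column. This stands: the mismatch is shown against v4.1 and the SAP text only.
- **The rates are assumed.** No document gives 1 or 2 events per patient-year, and lower rates show far less compression.
- **The named harms are single terms.** Protocol 1.3.6 reports hypotension in 6.0%, tachycardia in 6.5% and cardiac failure in 12.0% of cardiac patients on oral levosimendan, without giving exposure times. Rows at that level are not near saturation.
- **Nothing is lost from the record.** With at most 37 patients randomized in the parent study, recurrences can be counted by hand from the listings.
- **A raw event count does not show a trend.** The IV and oral periods differ in length, so counts without person-time would not show whether events become more or less frequent.

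A reader might infer that the safety tables cannot show recurrent harm at all, that percentages approach 100% for hypotension or heart failure, or that five years of follow-up are pooled throughout. The documents do not support this. Recurrences stay in the listings, the specific terms have their own rows, the two periods have separate columns, and the two-year limit applies to patients who remain on IV.

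None of these objections restores the event count to the SAP's tables or explains its absence.

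**Conclusion.** The point holds as a reporting mismatch on the primary endpoint. Against protocol v4.1, the SAP leaves out the number of TEAEs from all its adverse-event tables and declares no change. The practical loss is in the rows for any TEAE and any serious TEAE, where patient percentages compress differences in frequency. At the assumed 1 versus 2 events per patient-year, that means 86.5% versus 98.2% over 2 years, or 95.0% versus 99.8% over 3, while mean events double. For single preferred terms at low rates the loss is smaller.

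These sizes rest on assumed constant rates, equal follow-up and independent events. Clustering within patients would make the share of unreflected events larger. No test, power or sample size is affected. The correction should be made because the measure was promised and the data are already collected.

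**What to change.** 1. In Tables 14.3.1, 14.3.2.1, 14.3.2.3 and 14.3.2.4, add the number of events, patient-years and events per patient-year beside n (%), for the IV period, the oral period and the total. The exposure days already derived in SAP 3.3.5 can supply the patient-years. Patient-years are needed because the two periods differ in length.
2. Keep the maximum-severity summaries (Table 14.3.2.2 and the matching rows of 14.3.1) per patient, since maximum severity is a patient-level classification. The discontinuation tables (14.3.2.5 and 14.3.2.6) gain little from an event column and can stay as they are.
3. State in SAP 3.5.1 that contiguous records of the same preferred term in one patient, separated only by a severity change under protocol 9.1.1, count as one episode.
4. If event counts are not restored, list the omission in SAP section 4 as a departure from protocol 10.8, and check it against the wording of protocol v5.0.

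The cost is a few added columns and one derivation rule. No new data are needed.

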3.5.2 Clinical Laboratory Tests

Values and the associated change from baseline for each laboratory parameter will be calculated at each scheduled visit. Values considered to be abnormal (as defined by normal ranges) will be flagged for identification. All clinically significant lab values (hematology, chemistry and coagulation) will be presented in patient-level listings.

3.5.3 Vital Signs

Vital sign measurements (systolic blood pressure (SBP), diastolic blood pressure (DBP) and pulse rate (PR)) will be presented in patient-level listings.

3.5.4 *Electrocardiograms (ECGs)*

Abnormal ECG measurements will be presented in patient-level listings.

3.5.5 *Physical Examinations*

A patient-level listing of the physical examination assessments will be provided.

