2.3 Study Design

This extension study is designed to investigate the safety and efficacy of extended levosimendan in patients who previously received levosimendan in PH-HFpEF study sponsored by Tenax and may, in the investigator's opinion, derive benefit from continued treatment. Patients will be screened for eligibility at the last visit in the treatment period of the parent study. Eligible patients will be enrolled into the study immediately upon confirmation of eligibility so that levosimendan is not interrupted.

Efficacy assessments (6MWT, Patient global assessment (based on the KCCQ instrument), Physician's Assessment of Functional Class, Clinical Events; Death and hospitalizations) will be performed at 3, 6, 12, 24, 48, and yearly through Follow-up/Termination visit. For patients that transition from IV to oral (Week 0 and 6 or 8), the Time and Events Schedule for oral levosimendan should be followed. Patients will undergo a Follow-Up Visit (at termination) as soon as possible after study drug discontinuation, but within 2 weeks.

For patients that transition to oral levosimendan, the patient should be instructed to monitor their resting heart rate and blood pressure each day prior to the first dose. The patient should use the home monitoring device (provided at the initiation of the initial levosimendan study) to determine their resting heart rate and blood pressure after being seated at rest for at least 5 minutes. The heart rate and blood pressure readings should be recorded in the diary provided as well as the number of capsules the patient has taken each day. The patient should have their diary ready to review with the investigative site in each communication with the site and at office visits.

Patients whose BP falls below the specified range will be queried regarding any symptoms of hypotension which may result in the down titration of the levosimendan dose.

Patients whose heart rate exceeds the specified range will be queried regarding symptoms of worsening heart failure. An excessive heart rate in a patient with no evidence of worsening heart failure, suggests that the increased heart rate is a direct drug effect requiring adown titration of the levosimendan dose.

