14.5 ATTACHMENT 5: Patient Diary of Daily Heart Rate and Blood Pressure Readings

Week 0 through Week 2: (#) ____ capsules per day (#, as directed by physician)

Each morning, please monitor your blood pressure and heart rate. You should be sitting down and at rest **for at least five minutes** before taking your blood pressure and heart rate. The numbers you write down should be the same as those that appear on the monitor screen (do not round the numbers up or down). In the comments section, please write down anything that could have affected your reading, such as feeling unwell or changes in your medication.

NOTE: If your heart rate above 110 or your Systolic Blood Pressure is below 100, please call your doctor.

Date	Time	Heart Rate	Systolic BP (top number)	Diastolic BP (bottom number)	Study Drug # of capsules taken daily	PLEASE CHECK IF YOU ARE EXPERIENCING ANY OF THE FOLLOWING:
						 Palpitations  Light headedness  Chest pain  Worsening shortness of breath  Worsening edema (swelling)  Other _____
						 Palpitations  Light headedness  Chest pain  Worsening shortness of breath  Worsening edema (swelling)  Other _____

Week 2 through Week 4: (#) _____ capsules per day (#, as directed by physician)

Each morning, please monitor your blood pressure and heart rate. You should be sitting down and at rest **for at least five minutes** before taking your blood pressure and heart rate. The numbers you write down should be the same as those that appear on the monitor screen (do not round the numbers up or down). In the comments section, please write down anything that could have affected your reading, such as feeling unwell or changes in your medication.

NOTE: If your heart rate above 110 or your Systolic Blood Pressure is below 100, please call your doctor.

Date	Time	Heart Rate	Systolic BP (top number)	Diastolic BP (bottom number)	Study Drug # of capsules taken daily	PLEASE CHECK IF YOU ARE EXPERIENCING ANY OF THE FOLLOWING:

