3.2 Analysis Populations

3.2.1 Safety Analysis Set (SAF)

The Safety Analysis Set (SAF) will consist of all patients who receive at least 1 dose of study drug. Patients will be analyzed according to dose received, summarized by IV dosing period, oral dosing period, and in total. The SAF will be used for the analysis of safety data.

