3.4.1 Primary Endpoints

The primary endpoints (Safety measures) are as follows:

- Incidence and severity of treatment-emergent adverse events (TEAEs),
- Incidence and severity of abnormal clinical laboratory test results (hematology, chemistry),
- Incidence of abnormal physical examination results,
- Incidence of abnormal vital sign values (blood pressure [BP] and pulse rate [PR]), and
- Incidence of abnormal 12-lead electrocardiogram (ECG) results or values.

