3.5 Primary Endpoint Assessment

Primary endpoint safety measures will be summarized by treatment/dose group and overall using descriptive statistics (number of observations, mean, median, standard deviation, minimum, maximum) for continuous variables and counts and percentages for categorical data. Summaries will be based on the SAF. Associated patient-level listings will also be provided for the primary endpoint safety measures. Primary endpoint efficacy measures will not be summarized but will be provided in patient-level listings.

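### The primary blood pressure and pulse rate endpoint has no planned summary table, and the daily home diary has no place in the SAP

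*SAP*

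**What the plan says.** SAP 3.4.1 lists among the primary endpoints "Incidence of abnormal vital sign values (blood pressure [BP] and pulse rate [PR]), and" then the equivalent item for ECGs. SAP 3.5 states: "Primary endpoint safety measures will be summarized by treatment/dose group and overall using descriptive statistics". SAP 3.2.1 sets the grouping for the safety set: "Patients will be analyzed according to dose received, summarized by IV dosing period, oral dosing period, and in total". Protocol 10.8 agrees that a summary is intended: "Clinical laboratory tests, vital signs, and ECG findings will be summarized by treatment group and visit".

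The section that should deliver this, SAP 3.5.3, says: "Vital sign measurements (systolic blood pressure (SBP), diastolic blood pressure (DBP) and pulse rate (PR)) will be presented in patient-level listings". The list of tables and listings matches it. Vital signs have Listing 16.2.8.1 and no table, and no threshold for abnormal appears anywhere in the SAP.

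Protocol 2.3 has patients on oral treatment measure resting heart rate and BP each day before the first dose: "The heart rate and blood pressure readings should be recorded in the diary provided". Protocol 1.3.8.3 has investigators use these readings to guide titration. The form in Attachment 5 prints limits: "If your heart rate above 110 or your Systolic Blood Pressure is below 100, please call your doctor". Its last block covers Weeks 6 to 8, whereas protocol 2.3 gives no end date for daily monitoring and the synopsis provides 3 years of oral treatment. The SAP does not mention the diary.

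In the Time and Events Schedule, vital signs after the first oral dose fall at Weeks 2, 4 and 6, with Week 8 only for patients titrated at Week 6. Weeks 2 and 4 may be remote, with home-cuff values reported by phone.

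**The concern.** Protocol 1.3.6 names hypotension and tachycardia as the main safety events of interest for this drug. The BP and PR endpoint is where they would be counted objectively, yet the SAP promises an incidence and then supplies only a listing. A reader of the report would have to derive the numerator, the denominator and the definition of abnormal from patient-level data.

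The densest source of BP and heart rate data during titration, the diary, is also left undefined. Protocol Section 7 sends ongoing BP and heart rate documentation to the chart, and to the case report form where applicable, so the SAP does not settle whether diary values reach the database. Two things could then go wrong:

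- If an incidence is later produced from visit readings alone, it will rest on few days of the titration period.
- If diary values are merged into the vital-sign data, the oral period will have many more readings than the IV period, and its incidence will rise for that reason alone.

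**Working it through.** The plan states no detection rate, abnormality rate or sample size, so there is no figure to reproduce. The durations and rates below are assumptions, shown as ranges.

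**Share of titration days sampled.** The inputs are the Time and Events Schedule and protocol 2.3 (one diary reading a day).

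- Weeks 0–6: 3 visits / 42 days = 7.1%.
- Weeks 0–8: 4 visits / 56 days = 7.1%.

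An ongoing-protocol visit, timed from study entry, may occasionally add a reading.

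**Chance that a visit meets one abnormal episode of d consecutive days with a random start.** Two conventions are shown. The first requires the episode to lie wholly inside the window, with visits on days 14, 28, 42 (and 56), and divides the start days that touch a visit by all possible start days. The second ignores the window edges and uses d/14.

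| d (assumed) | 42 days, 3 visits | 56 days, 4 visits | d/14 |
|---|---|---|---|
| 1 | 3/42 = 7.1% | 4/56 = 7.1% | 7.1% |
| 3 | 7/40 = 17.5% | 10/54 = 18.5% | 21.4% |
| 5 | 11/38 = 28.9% | 16/52 = 30.8% | 35.7% |
| 7 | 15/36 = 41.7% | 22/50 = 44.0% | 50.0% |

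Under either convention, visit readings miss most episodes shorter than about a week.

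**Why the two sources should not be pooled.** With probability p of an abnormal value per reading, and readings treated as independent, P(at least one abnormal) = 1 − (1 − p)^n.

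| p (assumed) | n = 3 visits | n = 42 diary days | n = 4 visits | n = 56 diary days |
|---|---|---|---|---|
| 1% | 3.0% | 34.4% | 3.9% | 43.0% |
| 2% | 5.9% | 57.2% | 7.8% | 67.7% |
| 5% | 14.3% | 88.4% | 18.5% | 94.3% |

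The same underlying rate gives very different incidences purely through the number of readings. Real daily readings are correlated within a patient, which narrows the gap but does not change its direction.

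**What the diary itself can see.** It holds one pre-dose reading a day. An episode of h hours at a random time is met with probability h/24. The only duration the protocol gives for asymptomatic hypotension is a mean of 3.2 hours, from an earlier IV study (1.3.6): 3.2/24 = 13% for the diary, and 3.2/24/14 = about 1% for fortnightly visits.

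**Whether adverse events fill the gap.** Protocol 8.1.2.4 makes a vital-sign deviation an adverse event only if the investigator judges it clinically significant. Protocol 9.1.5 ties hypotension as an event of interest to a fall larger than the investigator anticipated. Attachment 3 leaves some asymptomatic readings beyond the diary limits at observation. A patient can therefore cross the printed limits without generating an adverse event.

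**The case against.** The strongest reply is that nothing is biased, because the SAP computes no BP or PR incidence from any source. A reader might infer that a planned primary incidence rests on three or four visit readings and leaves most transient episodes uncounted. The documents do not support that. SAP 3.5.3 plans a listing only, and this trial's episode rate and duration are unknown. There is also a working adverse-event route: the form tells patients to call, protocol 2.3 has sites review the diary and ask about symptoms, and clinically significant deviations become adverse events with tables in the SAP. This narrows the gap to readings not judged clinically significant.

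A reader might also infer that monitoring stops at Week 8, leaving all but 56 of 1,095 days (5.1%) of a 3-year oral period without daily readings. That is not established either. Protocol 2.3 has no end date and Section 7 asks for ongoing documentation. What is missing is a form beyond Week 8.

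Three further replies have some force:

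- SAP Section 5 says all available data will be listed, and programming specifications are in a separate document. But no diary listing is named, and a listing is not an incidence.
- SAP Section 4 cites protocol v5.0, while the protocol available is v4.1. SAP 2.2.1 omits the home-monitoring paragraph, so v5.0 may treat the diary differently. The missing BP and PR summary does not depend on this, because it is internal to the SAP.
- The diary would itself miss most episodes lasting only hours. That stands as a limit on what the fix can achieve.

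**Conclusion.** The point holds in two parts. First, a primary endpoint that SAP 3.4.1 and 3.5 say will be summarised has neither a table nor a cut-off in 3.5.3 or the output list. This follows from the text and needs no assumption. Second, the daily diary has no SAP rule, table or named listing, although its readings guide titration.

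Scheduled visits sample about 7% of titration days. Visit readings alone would catch 7% of one-day and about 42–50% of seven-day episodes, if episodes of those assumed lengths start at random times. The loss concerns abnormal readings not judged clinically significant; the others can reach the adverse-event tables. No formal comparison is planned, so the harm is to the completeness of the safety description and not to a test. It should be corrected before database lock.

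**What to change.** In SAP 3.5.3 and the output list:

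1. Add a table of the number and percentage of patients with abnormal BP or PR, by IV and oral period, from scheduled-visit readings only. State the cut-off and flag home-cuff values from remote Week 2 and 4 visits. Do not pool diary readings into this table.
2. Add a separate descriptive table and listing of diary readings for Weeks 0–8. Show patients with any, and with two or more consecutive, readings at SBP below 100 or heart rate above 110, and days beyond a limit divided by diary days with an entry. The limits are the form's own, used here only as reporting thresholds.
3. Reconcile protocol 2.3 (daily monitoring, no end date) with Attachment 5 (form ends at Week 8), and state in the report what home-reading data exist after Week 8.

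The cost is SAP wording, one or two tables, one listing and entry of diary rows not already in the case report form. An upper bound is 37 × 56 = 2,072 rows, if all 37 patients randomised in the parent study (protocol 1.3.5) transitioned and completed every day. The reported rate of abnormal readings will rise, and the text should say that this reflects added ascertainment.

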10.9 Efficacy Analysis

All efficacy endpoints are considered secondary endpoints. Descriptive statistics for efficacy endpoints will be reported at 3, 6, 12, 24, 48 and Follow-Up Visit (at termination) as well as Week 0 and Week 6 (or 8) for IV to oral transition patients.

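### Four of the SAP's five primary safety measures get listings but no summary table, and none of the four efficacy endpoints is tabulated

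*SAP*

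**What the plan says.** **Primary endpoint.** SAP Section 3.4.1 names five safety measures: TEAEs, laboratory tests, physical examination, vital signs and ECG. Each is an incidence; the vital-sign entry, for instance, reads "Incidence of abnormal vital sign values (blood pressure [BP] and pulse rate [PR". Section 3.5 then commits to an analysis: "Primary endpoint safety measures will be summarized by treatment/dose group and overall using descriptive statistics".

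**Planned outputs for the safety measures.** Section 3.5.1 gives counts and percentages for TEAEs. For the rest:
- Laboratory (3.5.2): "All clinically significant lab values (hematology, chemistry and coagulation) will be presented in patient-level listings".
- Vital signs (3.5.3): "Vital sign measurements (systolic blood pressure (SBP), diastolic blood pressure (DBP) and pulse rate (PR)) will be presented in patient-level listings".
- ECG (3.5.4): a listing of abnormal measurements.
- Physical examination (3.5.5): a listing.

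**Secondary endpoints.** SAP Section 3.4.2 says: "All Secondary Endpoint measurements will be presented in patient-level listings". Section 3.5 adds that efficacy measures will be listed and not summarized. It calls them primary there, although every efficacy endpoint in this study is secondary.

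**Protocol version 4.1.** Section 10.8: "Clinical laboratory tests, vital signs, and ECG findings will be summarized by treatment group and visit". Section 10.9: "Descriptive statistics for efficacy endpoints will be reported at 3, 6, 12, 24, 48 and Follow-Up Visit (at termination", with Week 0 and Week 6 (or 8) added for patients moving from IV to oral drug. The synopsis promises descriptive summaries of both safety and efficacy data.

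**Declared departures.** SAP Section 4: "This SAP does not deviate from the statistical analysis described in v5.0 of the protocol".

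**The concern.** An incidence needs a count of patients with the event and a count of patients assessed. The SAP defines its primary endpoint in those terms, says it will be summarized, and then plans no output that contains the two counts for four of the five measures. Run as written, the report could state the TEAE part of the primary endpoint and nothing numerical for the rest.

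Protocol Section 1.3.6 names hypotension and tachycardia as the safety events of main interest, so the lack of any blood pressure or pulse rate summary matters most. On the efficacy side, the secondary objective asks whether effectiveness is sustained over time. Listings of 6MWT, KCCQ and NYHA class do not answer that without by-visit values and within-patient change.

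**Working it through.** The documents state no sample size, alpha or power, so there is no figure to reproduce. The check is a tally of the SAP's list of tables and listings against the measures in Sections 3.4.1 and 3.4.2.

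**Step 1: tables.** Six tables cover disposition, deviations, demographics, IV exposure, oral exposure and concomitant medication (14.1.1 to 14.1.5). Seven cover TEAEs (14.3.1 and 14.3.2.1 to 14.3.2.6). 6 + 7 = 13.

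**Step 2: outputs per measure.**

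| Measure | Tables | Listings |
|---|---|---|
| TEAEs (primary) | 7 | 2 |
| Laboratory tests (primary) | 0 | 3, clinically significant values only |
| Vital signs (primary) | 0 | 1 |
| ECG (primary) | 0 | 1, abnormal only |
| Physical examination (primary) | 0 | 1 |
| 6MWT (secondary) | 0 | 1 |
| KCCQ (secondary) | 0 | 1 |
| NYHA class (secondary) | 0 | 1 |
| Death and hospitalization (secondary) | 0 | 0 |

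The 11 listings above plus 5 for disposition, deviations, demographics, exposure and medication give the 16 in the SAP. So 4 of 5 primary measures and 4 of 4 secondary endpoints have no summary table. Death and hospitalization also lack the listing that Section 3.4.2 promises for every secondary endpoint.

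**Step 3: can the listings stand in for the tables?**
- *Laboratory: no.* Section 3.5.2 defines abnormal by the normal range, but only clinically significant values are listed, and Protocol Section 8.1.2.5 treats these as a subset of out-of-range values. The count of abnormal results, the number tested at each visit and the shifts are all lost. Change from baseline is to be calculated, but no output shows it.
- *ECG: in part.* Patients with an abnormal ECG can be counted, but not how many had an ECG at each visit.
- *Vital signs and physical examination: by hand.* These listings are unrestricted. For vital signs, however, the SAP gives no rule for what counts as abnormal.

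**Step 4: which promise is broken?**
- Safety: the SAP contradicts itself (3.5 against 3.5.2 to 3.5.5 and the table list), whatever the protocol version. Protocol 10.8 adds a second conflict for laboratory tests, vital signs and ECG. It does not name physical examination; there the promise rests on SAP 3.5 and the protocol synopsis.
- Efficacy: SAP 3.4.2 and 3.5 agree on listings only. The conflict is with Protocol version 4.1, Section 10.9 and synopsis. SAP Section 3.4 still refers to efficacy analyses in the safety set and a per-protocol set, but the per-protocol set is never defined and no method is given.

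**The case against.** The best defense is that the important findings are counted elsewhere. Vital-sign deviations judged clinically significant are recorded as AEs (Protocol 8.1.2.4), hypotension and clinically significant arrhythmias are events of interest (9.1.5), and clinically significant laboratory changes can become AEs (9.1.6). All of these feed the TEAE tables. This stands in part: a reader might infer that hypotension and tachycardia would go uncounted, and that is not so. But the TEAE route depends on investigator judgment and measures something other than the incidence of abnormal values in Section 3.4.1.

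A second defense is scale. The study is descriptive, tests nothing, and draws on a parent study that randomized 37 patients, so hand counts are feasible. That holds for vital signs (once a threshold is fixed) and physical examination. It fails for laboratory shifts and for per-visit denominators of laboratory tests and ECG. SAP Section 5 does say that all available data will be listed, but the listing titles restrict laboratory and ECG output.

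A third defense concerns the protocol version. SAP Section 4 refers to version 5.0, and only 4.1 is available. The SAP's secondary objective covers oral drug only, while version 4.1 covers weekly IV and oral, so the text may have changed. A reader might infer that the no-deviation statement is false. Without version 5.0 that cannot be shown.

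**Conclusion.** The point holds. Four of five primary safety measures have no planned summary, against the SAP's own Section 3.5, and this does not depend on the protocol version. All four secondary endpoints also lack a summary, in conflict with Protocol version 4.1, and death and hospitalization have no dedicated table or listing; they surface only among serious TEAEs.

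Two stronger readings are not supported. A reader might take Section 3.5 as promising efficacy summaries too, but it says the opposite. A reader might also suppose that the listings show only patients who survive or stay on study. The SAP assigns the listings to all patients, so those who die or leave keep their earlier rows.

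The tally assumes that the SAP's output list is complete. Two sections defer details to a final SAP (3.3.4 and 3.5.1), but those details concern imputation of incomplete dates, not outputs.

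**What to change.** Add descriptive tables by IV period, oral period and total, matching SAP Section 3.2.1:

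- **(a) Laboratory:** by-visit value and change from baseline, and low/normal/high shift, on all results.
- **(b) SBP, DBP and pulse rate at clinic visits:** by-visit value and change, and n/N with an abnormal value under a prespecified threshold. The systolic and heart rate values in Protocol Attachment 3 could serve for counting only, with no change to clinical management. Attachment 3 gives none for diastolic pressure.
- **(c) ECG and physical examination:** abnormal n/N, with N the patients assessed.
- **(d) 6MWT, KCCQ and NYHA:** by-visit n, value and within-patient change, with the number still in follow-up shown. Use Week 0 as the reference for the oral period, because the SAP's single baseline (3.1.3) precedes the first dose of either form. It also helps with KCCQ, which replaced an earlier scale during the study, so some patients may have no KCCQ at entry.
- **(e) Death and hospitalization:** n/N and a listing.

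Then check SAP Section 4 against protocol version 5.0 and declare any remaining departure.

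The cost is modest. On one layout it is 2 + 2 + 2 + 3 + 1 = 10 tables and one listing, from data already scheduled for collection, with SAP text and programming but no new visits.
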